The study would be improved by targeting individuals with elevated stress/anxiety that drink to cope.

Response: As suggested, the revised proposal now targets individuals with elevated stress/anxiety (as done in our initial feasibility study, see **Preliminary Data**) as well as those who report drinking to cope with stress/anxiety as measured by the Drinking Motives Questionnaire - Revised (DMQ-R)^{1,2}. Additionally, the revised statistical analyses will directly examine the relationship between changes in stress/anxiety and alcohol use, as affected by pioglitazone.

Transdermal alcohol concentration (TAC) as measured by SCRAMx has limitations. Response: Reviewers' comments were mixed regarding the SCRAMx. However, we acknowledge limitations of the system and have removed the SCRAMx in the revised submission. Removal of SCRAMx has also allowed us to address concerns regarding the trial duration, which has now been increased from 4 weeks to 8 weeks, and fits well within the scope of an R21 project and budget.

Outcome measures related to alcohol consumption need to be operationalized and justified and the role of behavioral economic measures (delay discounting, alcohol demand) needs to be clarified. The revised submission now defines alcohol-related dependent measures as heavy drinking days in the past week (as highlighted by the Reviewers) and average drinks/day for the past week. Abstinence will be verified using ethyl glucuronide (ETG) test strips. The revised submission now clarifies that delay discounting and alcohol demand using a purchasing task will be assessed at weekly clinic visits to examine changes in craving and alcohol reward value, whereas a brief assessment of alcohol demand will examine changes in craving during the human laboratory model of stress reactivity. Previous studies have demonstrated that demand assessments are sensitive to experimental manipulations, including acute laboratory stress inducers³.

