Figure 1. Changes in stress reactivity (left panel) and weekly measures of stress/anxiety, alcohol craving, depressive symptoms, and alcohol consumption (right panel).

Overall Study Design. To accomplish the project aims, we will utilize a double-blind, mixed-model design with a between-groups factor of dose (pioglitazone vs. placebo) and a within-subjects factor of time. We will utilize urn-randomization based on gender and severity of alcohol use (AUDIT). A summary of the study timeline, procedures, and assessments is shown in **Table 1** below.

Table 1. Outline of Study Timeline, Procedures, and Assessments

Study Week	0	1	2	3	4	5	6	7	8
Procedures and Assessments	IRB	NU	BE						
Consent and Baseline Screening	IRB	APP	OVAL						

SCID, ASI, KMSK, TLFB, CIWAA, AUDIT	X								
Receive Study Medication (Pioglitazone or Placebo)	X	X	X	X	X	X	X	X	X
Assess Medication Compliance and Adverse Events		X	X	X	X	X	X	X	X
Brief Counseling	X	X	X	X	X	X	X	X	X
Human Laboratory Assessments (Specific Aim 1)									
Stress-Reactivity Assessment (Salivary Cortisol, HR, BP, self-report)	X				X				X
Alcohol craving (self-report, brief alcohol demand)	X				X				X
Weekly Assessments (Specific Aim 2)									
Alcohol Use and Craving (TLFB, BrAC, ETG, PACS, DMQ-R)	X	X	X	X	X	X	X	X	X
Stress and Anxiety (HAM-A, PSS, PCL-5)	X	X	X	X	X	X	X	X	X
Delay Discounting, Alcohol Demand (purchasing task)	X				X		X	X	X

SCID - Structured Clinical Interview for DSM-5, **ASI** - Addiction Severity Index⁶⁵; **KMSK** - Kreek-McHugh-Schluger-Kellogg scale⁶⁶; **TLFB** - Timeline Followback⁶⁷; **CIWAA** - Clinical Institute Withdrawal Assessment for Alcohol⁶⁸; **AUDIT** – Alcohol Use Identification Test⁶⁹; **BrAC** – Breath Alcohol Concentration; **ETG** – Ethyl Glucuronide; **PACS** – Pennsylvania Alcohol Craving Scale⁷⁰; **DMQ-R** – Drinking Motives Questionnaire Revised^{1,2}. **HR** – Heart Rate; **BP** – Blood Pressure; **HAM-A** – Hamilton Anxiety Rating Scale⁷¹; **PSS** – Perceived Stress Scale⁷²; **PCL-5** - PTSD Checklist for DSM-5⁷³.

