Recruitment. Recruitment strategies will include local advertising in print media, public service announcements on radio, and referrals to CNRA in the Houston metropolitan area. Additionally, we will utilize the University of Houston SONA system, which provides students credit for participating in various research studies. Access to SONA is made possible with the inclusion of [name] (Consultant). We will also recruit from the Department of Psychiatry Recruitment Registry: HSC-MS-23-0768.

Participants. We will enroll 60 participants to reach a target of **N = 50** completers (25/group). Participants will consist of otherwise healthy treatment-seeking individuals with AUD exhibiting elevated baseline stress/anxiety. All participants will meet the following inclusion and exclusion criteria:

Inclusion criteria. Be treatment-seeking individuals diagnosed with AUD (DSM-5); be at least 18 years old and fluent in English; past month excessive alcohol use (>7 drinks/week for woman, >14 drinks/week for men, >3 drinks/occasion for women>4 drinks/occasion for men)³⁵; exhibit baseline measures of either 1) 8-23 on HAM-A indicative of mild to moderate anxiety, 2) 14-26 on PSS Score indicative of moderate stress, or 3) ≥ 2 on DMQ-R questions related to drinking indicating that individuals drink at least “some of the time” to cope; and exhibit increased stress reactivity (increased physiological response and/or self-report) at the baseline stress reactivity assessment.

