Exclusion criteria. Exhibit severe scores on the HAM-A, PSS, or PTSD checklist (PCL-5) – may be enrolled at the discretion of the admitting physician ([name]); physical dependence on alcohol (CIWAA > 10); greater than mild substance use disorder on drugs other than alcohol, nicotine, and marijuana; contraindications for taking pioglitazone; medical conditions (e.g., congestive heart failure, clinically significant edema, clinically significant liver disease, hypoglycemia, diabetes, history of bladder cancer) contraindicating pioglitazone pharmacotherapy or taking contraindicated medications (e.g., CYP2C8 inhibitors or inducers, antihyperglycemic medications); be pregnant, nursing, or planning on becoming pregnant during the course of the study; females will need to agree to use of barrier methods of contraception due to pioglitazone’s effects on plasma concentrations of oral contraceptives; have any other illness, condition, or use of medications, which in the opinion of the PI and/or admitting physician would preclude safe and/or successful completion of the study.

Baseline Screening. Participants will receive a comprehensive medical and psychiatric evaluation including a medical-history questionnaire, physical examination, laboratory chemistries (e.g., blood chemistry screen, complete blood count, urinalysis and serum pregnancy test), and ECG. Clinicians will conduct the **SCID**, the **ASI**⁶⁵, the **KMSK**⁶⁶ assessment of lifetime substance use interview, and **TLFB**⁶⁷. Alcohol dependence will be assessed using the SCID and the **CIWA-A**⁷⁴. A CIWA-A score > 10 will be exclusionary.

Alcohol-Related Measures. Assessment of alcohol use will include self-report (**TLFB**) and **BrAC** (Alco-Sensor FST, Intoximeters, Inc., Saint Louis, MO). The TLFB will be used to assessed the occurrence of heavy drinking days (>3 drinks/occasion for women>4 drinks/occasion for men)³⁵ in the past 7 days and average drinks/day for the past 7 days. Severity of alcohol use will be assessed using the **AUDIT**⁶⁹. **Alcohol craving** will be assessed using a 4-item questionnaire⁷⁵ during the stress reactivity assessment and the **PACS** at weekly clinic visits. Motivations for drinking will be assessed using the **DMQ-R**¹, with demonstrated utility in the general^{2,76,77} as well as clinical^{78,79} populations. The DMQ-R consists of 20 questions assessing motivations for drinking that are rated on a 1 “almost never/never” to 6 “almost always/always” scale. **ETG** will

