Brief Counseling. At baseline, all participants will receive the NIAAA booklet "Rethinking Drinking: Alcohol and Your Health" providing research-based information related to alcohol use (RethinkingDrinking.niaaa.nih.gov). Study therapists will go over the booklet with the participant at the initial visit and at subsequent weekly visits using motivational interviewing techniques. At each visit, participants will also be assessed for recent alcohol use (self-report, ETG, BrAC), alcohol craving (PACS), and stress/anxiety (HAM-A, PSS). At the end of the study, referrals to local alcohol treatment services will be provided as needed.

Participant Payment & Compensation. Participants will receive \$50 for completing the baseline screening, \$25/visit for attending study visits (9 visits), \$25/assessment for completing stress reactivity

Table 2. Time Course for Assessing Stress-Induced Relapse Risk

Time (pm)	Study Procedures
3:00	Assess Craving, BAAD, Stress, Cortisol, HR, BP
3:15	Cold Pressor Task
3:20	Assess Craving, BAAD, Stress, HR, BP
3:45	Assess Craving, BAAD, Stress, Cortisol, HR, BP

assessments (3 assessments), \$10/week for medication compliance (8 weeks), and \$100 for completing the study (\$530 total). Participants will also receive \$5 compensation for busfare/parking at each study visit.

DATA ANALYTIC STRATEGY

Descriptive Statistics & Confounding Variables Descriptive statistics will evaluate measures of central tendency (continuous) and frequencies (categorical) for study-related variables. General variable relationships will be evaluated using correlation analyses. Preliminary analyses will inspect relationships between sample characteristics (e.g., demographics), predictor variables (e.g., inflammatory markers), and specified outcome variables (e.g., resilience measures) via traditional statistical tests (e.g., chi-square, Mann-Whitney-Wilcoxon, Kruskal-Wallis, and *t*-tests). Sample characteristic variables demonstrating a relationship with both the predictor and outcome variables in a given model will meet criteria as a potential confounder^{104,105} and included as a covariate in such models for hypothesis testing and explored as potential moderators of treatment group effects on experimental outcomes.

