Missingness & Multiple Comparisons Missing data will be addressed via maximum likelihood, explicit modeling of missingness, and/or imputation where appropriate. Each approach is robust to ignorable missingness (i.e. MCAR and MAR). Sensitivity analyses will permit evaluation of the robustness of findings to missing data assumptions. While Bayesian analyses are not influenced by traditional concerns of multiplicity, for the frequentist analyses, all primary outcome variables (those specified by name in the hypothesis statements below) will be evaluated at the $\alpha = 0.05$ statistical significance level. Secondary analyses will examine additional predictor and outcome variables (e.g., other inflammatory markers collected by assays); these and any otherwise *post hoc* analyses will employ false discovery rate (FDR) to control for Type I error.

Specific Analyses

Specific Aim 1: To examine the effects of pioglitazone on stress-induced relapse risk in a laboratory model. **Hypothesis 1a:** Participants receiving pioglitazone will show decreased stress reactivity (heart rate, blood pressure, salivary cortisol) compared to those receiving placebo. **Hypothesis 1b:** Participants receiving pioglitazone will show decreased alcohol craving (subjective, alcohol demand) compared to those receiving placebo.

For hypothesis 1a, GLMM will model each stress reactivity outcomes (primary: heart rate, blood pressure, and salivary cortisol) as a function of the main effects and higher-order interactions between time (baseline to Week 8), treatment (pioglitazone vs. placebo), and CPT measurement point (pre-CPT vs. post-CPT).

Follow-up analyses will examine lower-order interactions longitudinally as well as cross-sectional changes from pre- to post-CPT at each time point. Variable relationships and analyses for hypothesis 1b will follow the patterns stated above for Hypothesis 1a, with craving in place of stress reactivity.

Specific Aim 2: To examine the effects of pioglitazone on drinking, stress/anxiety, and alcohol craving in the natural environment. **Hypothesis 2a:** Participants receiving pioglitazone will show greater reductions in weekly psychometric measures of stress/anxiety measures: PSS and

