HAM-A) compared to those receiving placebo. **Hypothesis 2b:** Participants receiving pioglitazone will show greater reductions in weekly psychometric measures of alcohol craving (primary measures: PACS) compared to those receiving placebo. **Hypothesis 2c:** Participants receiving pioglitazone will show greater reductions in past week alcohol use (primary measures: heavy drinking days as defined by >3 drinks/occasion for women and >4 drinks/occasion for men, average drinks/day) compared to those receiving placebo.

For all hypotheses, GLMM will model primary outcome measures as a function of the main effects and interaction between treatment and time.

Sample Size and Power Considerations

Frequentist Analyses. Power for **Specific Aim 1** is based on the rate at which we may detect the three-way interaction between time, treatment, and CPT measurement point for a given measure of stress reactivity (transformed for normality) across $k = 1000$ Monte Carlo simulations (executed via SAS 9.4). Calculations assume the following conditions: $\alpha = 0.05$, an autocorrelation of $r = 0.50$ between consecutive observations (with a decay of $r = -0.10$ for subsequent observations), and a small correlation of $r = 0.05$ for observations occurring at the same time point across groups. Based on these assumptions, the different sample sizes (pragmatic and pessimistic) stipulated in **Table 3** each provide power to detect small-to-moderate effect sizes (treatment group differences expressed as Cohen's D, with effects unfolding in linear fashion over time). Power for **Specific Aim 2** is based on evaluating reductions in drinks per week. Estimates are derived using G*Power 3.1.9.2. Assuming $\alpha = 0.05$ (two-tailed) and an average baseline of drinks/week across participants (calculated as an average from 14 and 7 drinks/week for a 3:1 ratio of males to females, respectively), the different sample sizes (pragmatic and pessimistic) stipulated in **Table 3** each provide power to detect varying decreases in alcohol consumption.

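### The drinking outcomes rest on a 7-day look-back at each visit, and no rule says that the next interview covers the days of a missed, early or late visit

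*Combined protocol and SAP*

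**What the plan says.** - **Outcome definition.** Approach, Alcohol-Related Measures, uses the TLFB for heavy drinking days "in the past 7 days and average drinks/day for the past 7 days". The Introduction to the Revised Proposal gives the same definition: "heavy drinking days in the past week (as highlighted by the Reviewers) and average drinks/day for the past week".
- **Status.** Specific Analyses, Hypothesis 2c, reads "Participants receiving pioglitazone will show greater reductions in past week alcohol use" and names both measures as primary.
- **Schedule.** In Table 1 the row "Alcohol Use and Craving (TLFB, BrAC, ETG, PACS, DMQ-R") is marked at every week from 0 to 8. Brief Counseling ties the assessment to attendance: "At each visit, participants will also be assessed for recent alcohol use (self-report, ETG, BrAC").
- **Missing data.** Missingness & Multiple Comparisons works at the analysis stage: "Missing data will be addressed via maximum likelihood, explicit modeling of missingness, and/or imputation where appropriate". It adds "Each approach is robust to ignorable missingness (i.e. MCAR and MAR") and promises sensitivity analyses on the missing-data assumptions without specifying them.
- **What is absent.** The supplied text has no visit window, no make-up or telephone interview, and no statement of which days the TLFB covers after a missed or off-schedule visit. It does not forbid a longer look-back either.

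**The concern.** Staff who apply the stated window at each visit obtain a value for the 7 days before that visit and for no others. A participant who misses Week 3 and returns at Week 4 then has no Week 3 value, although the person is in the room and the calendar interview could reach back.

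The likely reason for absence matters more than the number of gaps. In people with alcohol use disorder, a heavy week is a plausible cause of a missed visit. Missingness would then depend on the unseen value itself, which is neither MCAR nor MAR. Maximum likelihood or imputation under MAR would not remove the resulting bias, and sensitivity analyses could show it but not supply the data. The outcomes affected are the trial's primary measures of drinking in daily life.

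**Working it through.** The plan states no figure on this point, so there is none to reproduce. The first two steps follow from its definitions. The rest is illustration, because the documents give neither a missed-visit rate nor drinking levels in missed weeks.

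**1. Off-schedule visits under a strict 7-day window.** A visit 10 days after the last one leaves 10 − 7 = 3 days uncovered. A visit after 5 days counts 7 − 5 = 2 days twice.

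**2. Which losses a longer look-back can reach.** The documents quantify only non-completion: 60 enrolled for 50 completers in Participants (10/60 = 16.7%), and 80 enrolled for 60 completers in section E.1.1 (20/80 = 25%). Weeks after dropout have no next visit. A longer look-back recovers intermittent gaps only.

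**3. Amount of information.** Among 50 completers over 8 weeks there are 50 × 8 = 400 person-weeks. If a share m of 5% to 20% is missed (assumed), 20 to 80 person-weeks have no drinking value.

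**4. Simple means.** Let R be drinking in missed weeks relative to attended weeks (assumed). Then true mean = observed mean × [(1 − m) + mR].
- m = 5%, R = 1.5: factor 1.025, so the observed mean is 1 − 1/1.025 = 2.4% too low.
- m = 20%, R = 2: factor 1.20, so it is 1 − 1/1.20 = 16.7% too low.
- R = 1: no bias.
- Equal m and R in both arms: the treatment ratio does not change.
- m = 5% on placebo and 15% on pioglitazone: a true ratio of 1.00 appears as 1.025/1.075 = 0.95 (R = 1.5) or 1.05/1.15 = 0.91 (R = 2), an apparent benefit where none exists.

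**5. Simulation of the treatment difference.** Assumptions: 3000 per arm, 8 weeks; heavy days Binomial(7, p) with person SD 1.2 and week SD 0.8 on the logit scale; pioglitazone multiplies p by 0.7; chance of a missed visit = expit(a + b × heavy days that week). The intercept was chosen and gives 2.50 and 1.77 heavy days/week, a true difference of −0.728. A random-intercept linear model is fitted to attended weeks.

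| (a, b) | Chance missed, 0 to 7 heavy days | Overall missed | Estimate | Shortfall |
|---|---|---|---|---|
| (−3, 0.2) | 5% to 17% | 7% | −0.713 | 0.015 (2%) |
| (−3, 0.35) | 5% to 37% | 11% | −0.677 | 0.051 (7%) |
| (−2.5, 0.35) | 8% to 49% | 17% | −0.655 | 0.073 (10%) |

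Repeat runs moved the shortfall by about one percentage point. Looking back to the last attended visit recovered about 85% of missed weeks and cut the shortfall to about 0.3% to 1.5%.

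**6. Size relative to noise.** Under the same model with 25 per arm and complete data, the standard error of the difference is about 0.37. The shortfalls are 0.015/0.37 = 4%, 0.051/0.37 = 14% and 0.073/0.37 = 20% of one standard error.

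The simulation looks at an average difference in a linear model. The plan tests a treatment-by-time interaction and allows count distributions, so these figures give an order of magnitude only.

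**The case against.** **The window defines the outcome, not the interview.** A reader might infer that drinking in a missed week is never recorded. The documents do not say so. The section states what the TLFB will be used to assess, not that questions stop at day 7. The TLFB also serves at screening, beside a criterion of "past month excessive alcohol use", so longer recall is not foreign to this trial. This stands: the defect is a missing instruction, and the loss is possible rather than stated.

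**Intermittent absence may be rare.** The pilot reports no missed visits, and attendance is paid: $25 per visit, $10 per week for compliance and $100 for completion. The pilot had 4 participants over 4 weeks, so it says little about 8 weeks at this size. Still, no document supports a particular rate, or a link between drinking and absence.

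**The plan has more than MAR methods.** It lists explicit modelling of missingness and sensitivity analyses. That is true, but neither is specified and neither collects a missing day.

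**The effect is small, and recovery has a price.** Both parts stand. The bias is a fraction of a standard error under the assumptions above. A recovered week has no ETG or BrAC sample from the missed visit, although the plan relies on ETG to verify abstinence, and its recall period is longer.

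**Conclusion.** The gap is real and modest. Both primary drinking outcomes use a past-7-day window at weekly visits, and no supplied text extends the interview to the last completed TLFB. Drinking in intermittently missed weeks, and on days around off-schedule visits, may be lost or double-counted.

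Bias arises only if absence depends on that week's drinking, which is an assumption. If so, the treatment difference is about 2% to 10% too small in the scenarios examined.

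Two stronger readings are not supported. One is that the next interview could recover all the missing drinking data: it cannot reach weeks after dropout, the only loss that the documents quantify. The other is that the bias must run towards no effect: if the pioglitazone arm missed more visits, it could exaggerate benefit. This is a cheap improvement to make prospectively and does not invalidate the design.

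**What to change.** - **Protocol, Alcohol-Related Measures:** state that each TLFB covers every day since the last completed TLFB, with no fixed 7-day limit.
- **Analysis plan, Hypothesis 2c:** derive heavy drinking days and average drinks/day for fixed study weeks (days 1–7, 8–14, and so on) from that daily record, so that an early or late visit neither drops nor repeats days.
- **Participants who stop attending:** attempt to collect the outstanding days by phone at last contact. Cell phones are already used to check adherence. This cannot cover later weeks, so dropout still needs the missing-data analysis.
- **Recovered weeks:** flag them, and run a sensitivity analysis without them.

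The cost is one protocol sentence, one derivation rule and a few interview minutes after a missed visit. The downsides are longer recall and no ETG or BrAC sample from the missed visit. Visits and sample size do not change.

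### A cheap gain in precision for Hypothesis 2c: replace the single 7-day baseline window with four separate pre-treatment weeks

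*Combined protocol and SAP*

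**What the plan says.** - **Outcome window.** The section on alcohol-related measures (Approach) takes both drinking outcomes from the TLFB "in the past 7 days and average drinks/day for the past 7 days". The introduction to the revised proposal gives the same definition: "heavy drinking days in the past week (as highlighted by the Reviewers) and average drinks/day for the past week".
- **Schedule.** In Table 1 the weekly row "Alcohol Use and Craving (TLFB, BrAC, ETG, PACS, DMQ-R" is marked at every visit from Week 0 to Week 8. The Week 0 outcome is therefore a 7-day value, and no longer baseline is defined.
- **Entry rule.** The inclusion criteria require "past month excessive alcohol use (>7 drinks/week for woman, >14 drinks/week for men", with per-occasion limits added. They do not name the instrument that establishes this.
- **Screening.** Table 1 lists "SCID, ASI, KMSK, TLFB, CIWAA, AUDIT" once, at Week 0. No look-back is given for that TLFB.
- **Analysis.** Under Specific Aim 2 in the section on specific analyses, "GLMM will model primary outcome measures as a function of the main effects and interaction between treatment and time". No baseline-drinking covariate is named, and the coding of time is not given.

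**The concern.** Hypothesis 2c is about greater reductions in drinking. In a treatment by time model, the Week 0 record is the only pre-treatment drinking information, so one week anchors each person's change. A single week may be untypical for someone about to enter treatment: it can be a binge week or one in which the person has already cut down. Noise in that anchor passes into the estimated change.

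The entry rule already turns on "past month excessive alcohol use", and a TLFB interview takes place at screening. A longer, still weekly, pre-treatment record is therefore within easy reach. With a target of 25 completers per group, and Table 3 aimed at decreases in consumption of 10% to 12%, precision gained without extra participants or visits is worth having.

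**Working it through.** **1. The plan's own figure.** Table 3 gives Aim 2 power for decreases of 12%, 11% and 10% as 97.8%, 95.2% and 90.8% at N = 50, and 88.6%, 82.5% and 74.6% at N = 40. The implied baseline is (3 × 14 + 7)/4 = 12.25 drinks/week. A two-group Poisson rate test with 7 weeks of exposure (an assumption) gives 98.2%, 95.9% and 91.9% at N = 50, which is close. At N = 40 it gives 95.2%, 91.2% and 85.2%, which is not. No single exposure reproduced both rows. The test family, exposure and variance are not stated, so this does not prove an error. Table 3 also has no term for baseline noise, so the change cannot be passed through it. The rest works with variance ratios, four baseline weeks against one.

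**2. Inputs.** Nine weekly records (Weeks 0 to 8) come from Table 1. Weekly correlation and linear time are assumptions. The only serial correlation in the documents is for Aim 1: 0.50 between consecutive observations, falling by 0.10 per further lag. It is borrowed here and floored at zero. Weekly variance is set to 1, the pre-treatment weeks share one mean, and the scale is linear (the plan would use a log link for counts).

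**3. Treatment by linear time, equal correlation r.** The slope variance is (1 − r)/Sxx, where Sxx is the sum of squared deviations of the time values.
- One baseline week, times 0 to 8: Sxx = 204 − 36²/9 = 60.
- Four baseline records at time 0, then 1 to 8: Sxx = 204 − 36²/12 = 96.
- Ratio 60/96 = 0.625, whatever r is.

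The change to Week 8 gives the same ratio: 2(1 − r) against 1.25(1 − r).

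**4. Change to Week 8, Aim 1 decay pattern.** Week 8 is uncorrelated with every pre-treatment week (lags 8 to 11).
- One week: 1 + 1 = 2.
- Variance of a four-week mean: [4 + 2(3 × 0.5 + 2 × 0.4 + 1 × 0.3)]/16 = 9.2/16 = 0.575. The change variance is 1.575.
- Ratio 1.575/2 = 0.79. Generalised least squares for the linear-time contrast also gives 0.79.

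**5. Linear-time contrast across assumed structures** (generalised least squares, four separate baseline records):

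| Assumed weekly correlation | Variance ratio | Reduction |
|---|---|---|
| Equal, 0.3 to 0.7 | 0.62–0.63 | about 37% |
| Random intercept plus AR(1) residual (0.3–0.6; 0.3–0.5) | 0.68–0.74 | 32% to 26% |
| Aim 1 decay pattern | 0.79 | 21% |
| AR(1) 0.5 | 0.74 | 26% |
| AR(1) 0.7 | 0.83 | 17% |
| AR(1) 0.9 | 0.96 | 4% |

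From a nominal 80% power, Φ(2.802/√ratio − 1.960) gives about 94% at 0.625, 88% at 0.79 and 82% at 0.96.

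**6. Baseline as covariate, four weeks entered separately.** With equal correlation the Week 8 residual variance is 1 − r² with one week and 1 − 4r²/(1 + 3r) with four. At r = 0.5 these are 0.75 and 0.60, ratio 0.80. At r = 0.3 and 0.7 the ratios are 0.89 and 0.72. Under the decay pattern or AR(1) the ratio is 0.99 to 1.00, whether the outcome is Week 8 or the Week 1–8 mean. There is no loss, but practically no gain.

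**7. Baseline as one 28-day mean covariate.** For the Week 1–8 mean outcome the ratio is 1.04 under the decay pattern. Under AR(1) of 0.5, 0.7 and 0.9 it is 1.03, 1.08 and 1.18. When correlation decays, the most recent week is the best predictor, and averaging dilutes it with older weeks.

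**The case against.** The case against is substantial, and much of it stands.

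- **The month of data is not shown to exist.** A reader might infer that the trial already collects a month of TLFB data and leaves it unused. The documents do not support that. The entry rule is past-month, but no instrument is named, and the SCID, ASI and KMSK are done at the same screening. The only TLFB window stated anywhere is 7 days.
- **Only the reference improves.** It is tempting to say that both outcomes become less noisy. They do not: the eight post-baseline weekly values are unchanged.
- **It is not free.** Recall over 28 days takes longer and is somewhat less exact than over 7. If heavy days became a 28-day count, the model would also need an offset or rescaling. Separate 7-day records avoid that last cost.
- **The gain is not known.** The 37% figure needs equal correlation and an unadjusted time contrast. The one correlation pattern in the documents decays with lag, and under full baseline adjustment that removes practically all of the gain.
- **Drinking may fall before entry.** Older, heavier weeks would then count pre-treatment decline as on-study reduction. The added weeks also belong to the entry window, so within-arm declines would contain some regression to the mean. Randomisation makes both similar across arms, but within-arm figures would need care.
- **The present design is coherent.** Identical 7-day windows at all nine visits are like for like, and AUDIT severity already enters the urn randomisation.

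What survives is the linear-time result: with separate records, every correlation structure tried gave a gain, and none gave a loss.

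**Conclusion.** This is an inexpensive improvement to the Hypothesis 2c analysis, not a mistake in it. The week-long baseline does not bias the treatment comparison, and nothing in the documents makes it invalid.

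In the planned treatment by time model with linear time, four separate pre-treatment weeks cut the contrast variance by about 37% (equal correlation), 21% (the Aim 1 pattern) or 26% down to 4% (AR(1) 0.5 to 0.9). With full baseline adjustment the result runs from a substantial gain under equal correlation to none under pure AR(1).

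These figures rest on an assumed weekly correlation, assumed linear time, a linear outcome scale and a common mean across the pre-treatment weeks. The documents fix none of these for drinking, so no single percentage should be quoted as the trial's gain.

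**What to change.** 1. State the look-back of the baseline TLFB and set it to the 28 days before Week 0.
2. In the Hypothesis 2c models, enter the four pre-treatment weeks as separate 7-day baseline records, or as four separate covariates. If drinking is falling before entry, add a pre-treatment week term common to both arms.
3. Do not use the 28-day mean as a single covariate.
4. State how time is coded and what within-person correlation is modelled.
5. Keep the post-baseline outcomes as weekly 7-day windows. For anyone already enrolled, use the screening TLFB where it covers the month.

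The cost is one or two sentences in the protocol and analysis section, a few more minutes of interview, and slightly less exact recall for the older weeks. Reports of within-arm decline should note that the baseline month overlaps the entry window.
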